To minimize the risk of a severe, immediate-type hypersensitivity reaction or capillary leak syndrome, the first dose of study agent will be administered in the Special Immunology Unit by personnel with experience administering rIL-2 to over 50 participants in the SILCAAT and ACTG 328 trials. Participants will be monitored for a minimum of 30 minutes following the first dose of study drug by personnel with life support training and access to adequate life support equipment and resuscitation medication.

Development of a grade ≥ 3 hypersensitivity reaction, a grade 2 hypersensitivity reaction that includes manifestations of angioedema, or suspected or confirmed capillary leak syndrome will require permanent treatment discontinuation.

E.1.3. Neutropenia

Participants who develop neutropenia will be referred for treatment by a qualified healthcare professional. Volunteers with an ANC $< 2,000$ cells/mm 3 at screening will be excluded.

- Should the ANC decrease to ≥ 500 but $\leq 1,000$ cells/mm 3 , the rIL-2 dose will be interrupted until the ANC is $> 1,000$ cells/mm 3 and then rIL-2 will be restarted at 3.5 million units twice daily. If the ANC then remains above 1,000 cells/mm 3 , this dose will be continued until the end of study.
- If the ANC drops to ≥ 500 but $\leq 1,000$ cells/mm 3 while on the reduced dose of 3.5 million units twice daily, rIL2 will be discontinued until the ANC reaches 1,000 cells/mm 3 , and then resumed at a dose of 2 million units twice daily. If the ANC then remains above 1,000 cells/mm 3 , this dose will be continued until the end of study. If the ANC falls again to $\leq 1,000$ cells/mm 3 while on the reduced 2 million unit twice daily dose, rIL2 will be permanently discontinued.
- Should the ANC decrease to < 500 cells/mm 3 , rIL-2 will be permanently discontinued.

E.1.4. Thrombocytopenia

Participants who develop thrombocytopenia will be referred for treatment by a qualified healthcare professional. Volunteers with platelet counts $< 150,000$ /mm 3 will be excluded.

- Should the platelet count decrease to $\geq 50,000$ but $\leq 100,000$ /mm 3 the rIL-2 dose will be interrupted until the platelet count is $> 100,000$ /mm 3 and then rIL-2 will be restarted at 3.5 million units twice daily. If the platelet count then remains above 100,000 /mm 3 , this dose will be continued until the end of study.

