Participants who develop pain, a skin rash, or other clinical manifestation deemed consistent with an episode of herpes zoster, will be immediately referred for evaluation by a qualified clinician, and will be required to discontinue study treatment until any pharmacologic treatment for varicella-zoster has been completed and the clinical manifestations have resolved in the judgment of the treating physician. Participants who develop recurrence of signs or symptoms or herpes zoster reactivation, and those who develop involvement of more than two dermatomes or have evidence of visceral involvement while on study will be required to discontinue study treatment permanently.

Participants who develop a detectable HBV DNA at any time during the study will be required to discontinue study treatment permanently, and will be referred for specialized medical care as soon as the study team becomes aware of a positive HBV DNA result.

E.1.10. Thrombotic Disease

At each visit, signs and symptoms of venous thrombosis will be sought. Participants who develop deep vein thrombosis or pulmonary embolism will permanently discontinue rIL-2 administration.

E.2. MANAGEMENT OF ADVERSE EVENTS ACCORDING TO SEVERITY

E.2.1. Grade 1 or 2 AEs

Participants who develop a Grade 1 or 2 AE may continue study treatment.

E.2.2. Grade 3 or 4 AEs

If the investigators have compelling evidence that the grade 3 or 4 AE has NOT been caused by the study treatment, dosing may continue without modification. In all other cases, the guidelines for dose adjustment will be applied. Refer to sections E.1 and C.6.2 and to Manual of Operations for dosing modification guidelines.

Participants experiencing Grade 3 or 4 AEs will be followed closely for resolution of the AE to

Grade ≤ 2.

E.3. PREGNANCY

Women of reproductive potential will be excluded from enrollment in the study. In the unlikely event that a participant does become pregnant while on study treatment (e.g., tubal ligation failure), study treatment will be permanently discontinued and the participant will be referred for immediate medical evaluation. Any such participants will be encouraged to remain in the study to be followed on study/off study treatment until study completion and will be followed by telephone contact thereafter to determine the pregnancy outcome. Pregnancy-related outcomes (health of the infant) and any pregnancy-related complications (e.g., fetal loss/abnormalities) will be reported on the CRF.

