 - Lymphoma, primary of brain
 - Progressive multifocal leukoencephalopathy
 - Toxoplasmosis of brain
- Occurrence of herpes zoster reactivation involving more than two dermatomes or visceral involvement including but not limited to viral pneumonia, encephalitis and hepatitis.
- Occurrence of a serious infection that is considered life-threatening or requires inpatient treatment.
- Occurrence of an incident cancer other than a localized basal cell carcinoma of the skin that requires local excision only.
- Requirement for prohibited concomitant medications (see exclusion criteria and section C.6).
- Pregnancy or breastfeeding.
- Deep vein thrombosis or pulmonary embolism.
- Myocardial infarction or other acute coronary syndrome.
- Development of a grade ≥ 3 hypersensitivity reaction, OR a grade 2 hypersensitivity reaction that includes manifestations of angioedema, or suspected or confirmed capillary leak syndrome.
- Development of an ANC < 500 cells/mm³.
- Development of a platelet count $< 50,000$ /mm³.
- Elevation of AST or ALT to > 5 x ULN.
- Serum TSH elevation to ≥ 3.99 mIU/L, abnormal serum T4 or T3 levels, abnormal levels of anti-Tpo antibodies, or symptomatic hypo- or hyperthyroidism.
- Completion of treatment as defined in the protocol.
- Request by participant or his/her healthcare providers to terminate treatment.
- Reasons believed to be clinically significant by the investigators, even if not addressed in the adverse event management section of the protocol.

F.2. PREMATURE STUDY DISCONTINUATION

- Failure by the participant to attend 3 consecutive visits.
- Request by participant or his/her healthcare providers to terminate participation in the study.
- Participant judged by the investigator to be at significant risk of failing to comply with the provisions of the protocol as to cause harm to self or seriously interfere with the validity of the study results.
- At the discretion of the institutional review board (IRB), Office for Human Research Protections (OHRP), FDA, NIAID or investigator.

F.3. TEMPORARY TREATMENT DISCONTINUATION

- Criteria for withholding dose met (refer to section C.5.2 and to Manual of Operations).

G. SAFETY MONITORING

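### E.2.2 lets dosing continue after an unrelated grade 3-4 event, while E.1 and F.1 impose mandatory stops with no cause condition, and no text says which governs

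*Combined protocol and SAP*

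**What the plan says.** Section E.2 sets the dosing rule by severity. For the lower grades, E.2.1 reads: "Participants who develop a Grade 1 or 2 AE may continue study treatment". For grade 3 or 4, E.2.2 says that where the investigators have "compelling evidence that the grade 3 or 4 AE has NOT been caused by the study treatment, dosing may continue without modification". It then adds: "In all other cases, the guidelines for dose adjustment will be applied", and closes with "Refer to sections E.1 and C.6.2" and the Manual of Operations as the sources for modifying doses. The protocol text has no C.6.2; the dose-modification guidelines are in C.5.2.

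Sections E.1 and F.1 set stops by event. E.1.2 lists hypersensitivity of grade 3 or higher and then "a grade 2 hypersensitivity reaction that includes manifestations of angioedema, or suspected or confirmed capillary leak syndrome will require permanent treatment discontinuation". F.1 repeats both triggers, the second as "OR a grade 2 hypersensitivity reaction that includes manifestations of angioedema". Neither makes the stop depend on cause. E.1.3, E.1.4, E.1.5 and E.1.10, together with F.1, likewise stop treatment permanently for ANC below 500, platelets below 50,000, AST or ALT above 5 times ULN, and DVT or PE. F.1 alone adds "Myocardial infarction or other acute coronary syndrome".

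Section I.6.1.2 states the allergy stop differently: it covers severe reactions that are related to study treatment.

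**The concern.** E.2.2 sorts grade 3-4 events by cause before anything else. An event convincingly attributed elsewhere goes straight to unmodified dosing, and the guidelines for which E.2.2 cites E.1 are reached only for the rest. Read as written, an unrelated event bypasses E.1. E.1 and F.1 do not sort by cause at all. A site can therefore find a permission to continue at full dose and a mandatory stop for the same event.

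What is at stake is participant safety and uniform handling. Under C.5.1.2 all eight doses of a cycle are normally handed over on day 0, and under D.2.9 staff contact on days 2 and 4 is by telephone. Staff deciding whether the remaining syringes may be used need one rule.

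**Working it through.** No figure in the plan bears on this point, so the check sets the rules side by side. The inputs are E.2.1, E.2.2, E.1.2-E.1.5, E.1.10 and F.1.

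| Event | E.2 on its face | E.1 / F.1 | Result |
|---|---|---|---|
| Grade 3-4 hypersensitivity, compelling evidence of another cause | E.2.2: may continue, unmodified | E.1.2, F.1: permanent stop | Explicit conflict |
| Grade 3-4 hypersensitivity, no such evidence | E.2.2: use the guidelines, citing E.1 | E.1.2, F.1: permanent stop | No conflict |
| Grade 2 hypersensitivity with angioedema | E.2.1: may continue | E.1.2, F.1: permanent stop | No carve-out, but the specific rule most likely governs |
| AST/ALT >5 x ULN, ANC <500, platelets <50,000, DVT/PE, shown to be unrelated | E.2.1 or E.2.2, depending on grade | E.1 and F.1: permanent stop | Conditional on grade |
| MI/ACS, shown to be unrelated | E.2.1 or E.2.2, depending on grade | F.1 only: permanent stop | Conditional on grade; E.2 does not cite F.1 |

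The first row is explicit because the protocol prints the grade on both sides. An example would be a severe reaction to a newly started antibiotic. The last two rows are conditional because the protocol grades events by an external DAIDS table that it does not reproduce.

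Next, does any sentence rank the rules?

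- The opening of E.1 applies the C.5.2 guidelines to the E.1 scenarios. It does not mention E.2.
- C.5.2 gives the investigator's judgment precedence, but only for treating further toxicities as dose-limiting.
- Section G has investigators check every event of grade 2 or higher against the discontinuation criteria. It does not say what to do when E.2.2 permits dosing.
- The last bullet of F.1 allows stops for other clinically significant reasons, "even if not addressed in the adverse event management section of the protocol". That shows that F.1 reaches beyond section E, but it does not rank the two.

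None of these settles the E.2.2 case, and I.6.1.2 adds doubt by making relatedness part of the allergy stop.

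Effect on the analysis (C.2.1): the primary set is everyone with at least one dose, so a later stop does not change membership. The on-treatment set (all eight cycles) and the number-of-cycles term could change. One participant is 1/20 = 5% of the planned enrolment.

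**The case against.** The strongest reply is that permission is not contradiction. E.2 says that dosing may continue, while E.1 and F.1 are mandatory, so stopping complies with both. E.1 is also the specific section and E.2 the general one. Naming grade 2 hypersensitivity with angioedema in E.1.2 and F.1 would serve no purpose if E.2.1 prevailed. Section G adds a real-time check against the discontinuation criteria with no attribution condition, and several stops are repeated in section I.6. For the grade 2 case this largely succeeds. A reader might infer that the two hypersensitivity cases are equally firm; the documents do not support that.

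It does not dispose of the E.2.2 case. There the text itself sends unrelated events away from the guidelines it takes from E.1. It can be argued that I.6.1.2 limits the stop to related reactions, so that E.2.2 and the stop agree. But E.1.2 and F.1 carry no such limit, so that argument moves the inconsistency rather than removing it.

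Two further points stand. The Manual of Operations, to which E.2.2 also refers, is not among the documents and may contain a precedence rule. And the threshold of compelling evidence is demanding, so few events should meet it.

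A reader might also gauge the problem by the doses at stake. The schedule is 2 x 4 x 8 = 64 doses, so a stop after the first dose leaves 64 - 1 = 63 ungiven. That is schedule arithmetic true of any early stop. It measures neither the probability nor the harm of wrongful dosing.

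**Conclusion.** The point holds as a minor-to-moderate conflict between stated safety rules. It is explicit for grade 3 or higher hypersensitivity attributed to another cause. It is conditional on grade for the other stops. For grade 2 hypersensitivity with angioedema it is a missing carve-out that the specific stop and section G would most likely resolve. E.1 and F.1 are probably meant to prevail throughout, but for unrelated grade 3-4 events the reader has to infer this against the wording of E.2.2.

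A reader might infer that the protocol authorises re-dosing after every mandatory stop, for instance after any DVT. It does not: E.2.2 needs compelling evidence of another cause, and which E.2 rule applies depends on the external grading table. Frequency cannot be estimated from the documents and is probably low in at most 20 participants. The effect on the analysis is negligible. The conclusion assumes that the Manual of Operations does not already settle precedence.

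**What to change.** Add to both E.2.1 and E.2.2: *except where E.1 or F.1 requires interruption or permanent discontinuation, in which case E.1/F.1 governs*. The clause should not say that the stops apply regardless of grade, because the hypersensitivity stop is itself defined by grade.

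Correct the reference in E.2.2 from C.6.2 to C.5.2, and align the hypersensitivity bullet in I.6.1.2 with E.1.2 and F.1. Whether an allergic reaction proven to have another cause should end treatment is a clinical choice. If the sponsor wants to allow continued dosing there, the condition belongs in E.1.2 and F.1 themselves.

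The cost is two clauses, one corrected cross-reference and one reworded bullet, with no added visits, procedures or data.

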11. Use of chronic corticosteroids, hydroxyurea, or immune-modulating agents (e.g., interleukin-2, interferon-alpha or gamma, granulocyte colony stimulating factors, etc.) within 30 days prior to enrollment.
NOTE: Use of inhaled or topical steroids is not exclusionary.
12. Breast-feeding.
13. Use of aspirin, warfarin or any other antithrombotic or antiplatelet agent during the 2-week period prior to leukapheresis.
14. History of autoimmune disorders, including but not limited to Crohn's disease, scleroderma, thyroiditis, inflammatory arthritis, myasthenia gravis, glomerulonephritis, systemic lupus erythematosus, and vasculitis.
15. Type 1 diabetes mellitus.
16. History of thyroid disease that has required antithyroid or thyroid hormone replacement therapy at any time in the past.
17. Current continued use, or anticipated continued medical indication for nephrotoxic agents, including but not limited to aminoglycosides and other potentially nephrotoxic antimicrobials, indomethacin, high scheduled doses of other NSAIDs, and lithium salts.
NOTE: Low doses or limited duration of these agents (i.e., ≤14 days) is not exclusionary.
18. Current continued use, or anticipated continued medical indication for hepatotoxic agents, including but not limited to amiodarone, methotrexate, and anticonvulsants and antimicrobials with elevated hepatotoxic potential.
NOTE: Low doses or limited duration of these agents (i.e., ≤14 days) is not exclusionary.
19. Active drug or alcohol use or dependence that, in the opinion of the investigator, would interfere with adherence to study requirements.
20. Serious illness requiring systemic treatment and/or hospitalization within 30 days prior to study entry that in the judgement of the investigator may compromise study participation or pose additional risks to the participant.
21. Any other condition that, in the opinion of the clinical investigator or sponsor, might compromise any aspect of this trial.

Study Treatment

All 20 participants will receive subcutaneous rIL-2 therapy in addition to combination antiretroviral therapy. Any combination of three FDA-approved antiretrovirals may be used.

Recombinant IL-2 at a dose of 5 MIU twice daily will be given subcutaneously for 4 consecutive days every 8 weeks for eight cycles.

Blood will be drawn for CD4 cell counts, for viral load, for routine safety monitoring and for HIV reservoir assays as detailed in section D.3.5 of the protocol.

Safety Monitoring

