The screening visit will occur 8-16 weeks prior to start of rIL-2 treatment, and will include:

- History and complete physical examination that includes evaluation of adequate venous access for leukapheresis
- Height and weight measurements
- Concomitant medication review
- CBC and metabolic panel
- Pregnancy test
- Thyroid function tests and anti-Tpo antibodies
- CD4+ and CD8+ T cell count (both absolute and as percent of lymphocytes).
- Plasma HIV RNA level (using the locally available assay) and verification that plasma HIV RNA levels prior to screening meet the inclusion criteria.
- Hepatitis B and C testing
- Informed consent

D.2.2. Leukapheresis Visit

The pre-treatment leukapheresis visit will occur 4-8 weeks prior to start of rIL-2 treatment, and will include:

- Interval history and targeted physical examination
- Concomitant medication review.
- CBC and metabolic panel
- CD4+ and CD8+ T cell count (both absolute and as percent of lymphocytes) and documentation of all interim CD4+ counts (absolute and percents).
- Thyroid function tests and anti-Tpo antibodies.
- Participant will be instructed as to how IL-2 will be injected subcutaneously. Instructions for preparing rIL-2 for administration are given in the Manual of Operations, which includes the Investigator's Brochure as an appendix. Participants receiving rIL-2 will be taught to give themselves injections. Participants will be given a dosing log for future use and will be encouraged to refer to it during their daily activities. Supporting materials for clinical staff and for participants on administering rIL-2 and managing expected side effects are included in the Manual of Operations. The Manual of Operations also includes contact information for questions concerning clinical management. No rIL-2 will be administered at this visit.
- A 4 liter leukapheresis will be performed at the Seidman Ambulatory Stem Cell Transplant

Unit at University Hospitals using AIDS protocol 328.

- Plasma will be frozen for single copy HIV RNA assay.
- Leukapheresis samples will be processed into PBMC that will be cryopreserved for assays of:
 - HIV reservoir by QVOA
 - HIV reservoir by EDITS
 - Total and intact proviral DNA assay (Accelavir)
 - Immune Cell Phenotype
 - NK cell phenotype

D.2.3. rIL-2 Initial Treatment Visit – Cycle 1, Day 0

The first IL-2 cycle will start 4-8 weeks after the leukapheresis visit and will include:

- Interval history and targeted physical examination, including weight.

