Staff will contact the participant by phone to assess tolerance and compliance with injection schedule

D.2.10. End of Study Visit (or Premature Discontinuation Visit)

NOTE: The end of study visit should take place 8 weeks (+/- 2 weeks) after Day 0 of the last (8th) treatment cycle. In the case of premature discontinuation, the end of study visit should take place at least 6 weeks after day 0 of the last treatment cycle and may take place up to 10 weeks after day 0 of the last treatment cycle.

These visits will include:

- Interval history and targeted physical examination.
- Immunogenicity testing
- CD4+ and CD8+ T cell count (both absolute and as percent of lymphocytes)
- Plasma HIV RNA level by PCR (using the locally available assay)
- IL-2 immunogenicity
- At this visit the participant will undergo a 4 Liter leukapheresis at the Seidman Ambulatory Stem Cell Transplant Unit at University Hospitals using AIDS protocol 328.
- Plasma will be cryopreserved for single copy HIV RNA assay
- Leukapheresis product PBMC will be cryopreserved for:
 - HIV reservoir assay by EDITS
 - HIV reservoir assay by QVOA
 - Total and intact proviral DNA assay (Accelavir)
 - Assays of immune cell phenotype and NK cell phenotype

If leukapheresis cannot be done after premature treatment discontinuation for any reason, a 120 cc. blood draw will be obtained for preparation of PBMC and plasma. Based upon cell yield these samples will be used for:

- Plasma will be cryopreserved for single copy HIV RNA assay
- HIV reservoir assay by EDITS
- HIV reservoir assay by QVOA
- Total and intact proviral DNA assay (Accelavir)
- Assays of immune cell phenotype and NK cell phenotype

D.2.11. Immunogenicity follow-up

Participants who have detectable neutralizing antibodies at the end of study visit will be followed approximately every 90 days for repeat testing until 12 months after the end of study or until a negative result is obtained. During these visits, an interval medical history and targeted physical exam will be conducted. If clinically significant events have occurred, the participant will be referred for appropriate medical care.

D.2.12. Management of off-window visits

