All adverse events grade 2 or greater will be reviewed in real time by the study investigators, who will establish their relationship to study treatment (see below). The study investigators will also determine whether specific treatment for each adverse event is warranted, whether they meet criteria for study treatment discontinuation, and whether they constitute an emerging exclusionary criterion.

In addition to the real-time review of adverse events, the study data manager and statistician will prepare a bi-yearly report of accrual, early study treatment and study discontinuations (and related reasons), baseline characteristics, longitudinal CD4 T cell count and plasma HIV RNA measurements, Grade ≥ 2 signs and symptoms, Grade ≥ 2 laboratory abnormalities and reported serious adverse events (SAEs). This report will be reviewed by the research team and the Safety Monitoring Committee (SMC) during regularly scheduled conference calls every 6 months. The investigators and SMC chair may jointly forgo an actual conference call if the reports have been reviewed and no additional discussion is deemed necessary.

In addition to the regularly scheduled reviews, the SMC will perform expedited reviews of the safety data whenever any of the following happens:

- Two or more participants have experienced a grade 4 AE that is deemed possibly, probably, or definitely related to study treatment
- Any death occurs on study that is deemed possibly, probably, or definitely related to study treatment

Whenever either of the two criteria immediately above occurs, enrollment into the study will be paused until the SMC review has taken place and a determination has been made that enrollment can resume.

The SMC will be composed of an investigator affiliated with Case Western Reserve University in a department other than the Division of Infectious Diseases and HIV Medicine, an investigator not affiliated with Case Western Reserve University, and a biostatistician with no direct responsibilities managing trial-derived data.

H. DATA COLLECTION AND MONITORING AND ADVERSE EVENT REPORTING

H.1. RECORDS TO BE KEPT

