- Previous report of similar AEs associated with rIL2
- Recurrence of the AE after re-challenge or resolution after de-challenge.

The terms used to assess the relationship of an event to rIL2 are:

- Definitely related – The AE is **clearly related** to rIL2
- Probably related – The AE is **likely related** to rIL2
- Possibly related – The AE **may be related** to rIL2

- Probably not related – The AE is **not likely related** to rIL2
- Not related – The AE is **clearly NOT related** to rIL2

When an AE is assessed as “not related” to rIL2, an alternative etiology, diagnosis or explanation for the AE will be provided. If new information becomes available, the relationship to assessment of any AE will be reviewed and updated, as required.

H.3.8. Expedited AE Reporting Period

The protocol-defined EAE Reporting Period for this protocol is the entire study duration for an individual participant (from study enrollment until study completion or discontinuation of the participant from study participation for any reason). After the protocol-defined AE reporting period, unless otherwise noted, only SUSARs as defined in Version 2.0 of the DAIDS EAE Manual will be reported if the study staff become aware of the events on a passive basis (from publicly available information).

H.3.9. Reporting Procedures

All participants will be followed for possible adverse events throughout their involvement in the study, including issues with study conduct. At each study visit, research staff will elicit participant input as to discomforts or adverse experiences. All grade ≥ 2 AEs will be reported to the Principal Investigators on a daily basis. A complete blood count, metabolic panel as defined in D.3.5.1, CD4 T cell count, and plasma HIV-1 RNA level will be performed on most visits. The Principal Investigator will obtain these safety data in “real-time” (i.e., within 1-10 days of a study visit) when laboratory values become available. The Principal Investigators will review these data within that timeframe, assess degree of severity, and assess the relationship to study agent/intervention.

The following adverse events will be reported: adverse events graded 3 and above, and any possibly, probably, or definitely related, unexpected, and serious adverse events. These AEs will be reported to the Safety Monitoring Committee (SMC), and FDA. Reporting to the UHCMC IRB will follow current UHCMC IRB policy (see section H.4.3).

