The SMC will review accrual, toxicity summaries, off-treatment and off-study rates, and reasons broken down by study arms. Meetings of the SMC are described above. The SMC will be asked to consider the following regarding safety events: the grade of the event, the time to resolution (if any), and the site clinician's judgment of the relationship to treatment. The first interim safety review by the SMC is planned 3 months after the first subject enrolls and approximately every 3 months thereafter, but expedited reviews will occur whenever the threshold for temporary enrollment discontinuation is reached. Criteria for temporary enrollment discontinuation and expedited SMC review are:

- Three or more participants have experienced a grade 3 AE that is deemed possibly, probably, or definitely related to study treatment
- Two or more participants have experienced a grade 4 AE that is deemed possibly, probably, or definitely related to study treatment
- Any death occurs on study that is deemed possibly, probably, or definitely related to study treatment

The SMC will review the events whenever any of the criteria above is met, and recommend, based on the results of the review, whether the study can proceed as planned, proceed with modifications, or be discontinued.

I.4. Human Subjects Involvement, Characteristics, and Design

Up to 20 participants will be enrolled in the clinical trial. Potential participants will be recruited primarily from the Special Immunology Unit, the HIV clinic of University Hospitals Cleveland Medical Center, although recruitment from other area hospitals through direct outreach and targeted advertisement is also possible. Characteristics of the study population, inclusion/exclusion criteria, and planned study procedures are described in the clinical protocol. No vulnerable populations will be included in these studies.

I.5. Sources of Materials

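### The SMC review and enrolment-pause triggers count only rIL-2-related events, so a death or repeated severe events caused purely by leukapheresis meet none, out of line with H.3.2 and I.10

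*Combined protocol and SAP*

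**What the plan says.** **Triggers.** Section G lists two events that bring an expedited SMC review: "Two or more participants have experienced a grade 4 AE that is deemed possibly, probably, or definitely related to study treatment" and "Any death occurs on study that is deemed possibly, probably, or definitely related to study treatment". When either occurs, "enrollment into the study will be paused until the SMC review has taken place". Section I.3 repeats both and adds a third: "Three or more participants have experienced a grade 3 AE that is deemed possibly, probably, or definitely related to study treatment".

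**What counts as study treatment.** Under Study Treatment, the synopsis states: "All 20 participants will receive subcutaneous rIL-2 therapy in addition to combination antiretroviral therapy". H.3.7 opens its five-level causality scale with "The terms used to assess the relationship of an event to rIL2 are" and provides no scale for procedures. I.7.2 names treatments and procedures as separate sources of risk.

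**The procedure.** D.2.2 states: "The pre-treatment leukapheresis visit will occur 4-8 weeks prior to start of rIL-2 treatment". It specifies 4 litres. D.2.10 adds the second, at the end-of-study visit: "At this visit the participant will undergo a 4 Liter leukapheresis".

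**Where procedures are recognised.** H.3.2 requires notice to the SMC Chair within 3 reporting days of a death judged related to the study drug or to a study procedure, if it occurs in the treatment phase or within 30 days of the last dose. I.10 has the two principal investigators determine how adverse events relate to study procedures.

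**The concern.** Leukapheresis is required twice by the protocol and is done for research. The protocol treats it as carrying risk: eligibility requires adequate venous access and no contraindication to it, and excludes recent antithrombotic or antiplatelet use beforehand.

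The written triggers leave it out. If a participant died from the baseline procedure, no criterion in G or I.3 would be met, and nothing would automatically halt enrolment, and with it further baseline leukaphereses, while the SMC looked at the case. Pre-specified triggers are meant to keep that step from depending on someone's discretion. H.3.2 and I.10 show that the authors regarded relatedness to procedures as relevant to safety oversight, so the narrower scope in G and I.3 looks like an inconsistency and not a considered exclusion.

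**Working it through.** The plan states no operating characteristic for these triggers, so there is no figure to reproduce. The check compares the sections and adds date arithmetic.

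**1. Number of procedures.** 2 per participant × 20 participants = 40 at most.

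**2. Baseline procedure (D.2.2).** 4-8 weeks before the first dose is 4 × 7 = 28 to 8 × 7 = 56 days. No rIL-2 has been given, so no complication of it can be related to rIL-2.

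**3. End-of-study procedure (D.2.10).** 8 ± 2 weeks after day 0 of the last cycle is 42 to 70 days. A cycle is 4 consecutive days from day 0, so the last dose falls on day 3, or on day 4 if the first dose is late in the day.
- Last dose on day 3: 42 − 3 = 39 to 70 − 3 = 67 days after it.
- Last dose on day 4: 42 − 4 = 38 to 70 − 4 = 66 days after it.

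The premature-discontinuation visit has the same 6-10 week range.

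**4. The H.3.2 window.** Its limit is 30 days after the last dose; the shortest gap is 38 days, so the end-of-study procedure lies at least 8 days outside. The baseline procedure precedes that participant's treatment. If the treatment phase is read per participant, both are missed. If it is read as the phase of the whole study, H.3.2 could reach them; the text does not say which is meant.

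This step uses the visit schedule. C.2.1 places the final reservoir measurement two weeks after the last rIL-2. No leukapheresis is scheduled then, but one at 14 days would fall inside the 30-day window.

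**5. Purely leukapheresis-related events against each rule.**

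| Event | G | I.3 |
|---|---|---|
| One death | not met | not met |
| Grade 4 in two or more participants | not met | not met |
| Grade 3 in three or more participants | no such trigger | not met |

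| Other provision | Reaches the event? | Automatic pause or SMC review? |
|---|---|---|
| H.3.2 notice of death to SMC Chair | depends on step 4 | no |
| H.3.9 grade 3 and above reports to SMC and FDA | yes, any cause | no |
| H.3.3 deaths to the IRB within 7 days | yes | no |
| F.2 and I.3 powers to stop | yes, by discretion | no |

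**6. Illustration under assumed rates.** Suppose procedures counted, and let p be the assumed per-participant risk of a procedure-related grade 4 event. The grade 4 trigger would fire with probability 1 − (1 − p)^20 − 20p(1 − p)^19. At p = 1% this is 1 − 0.818 − 0.165 = 0.017; at 0.5% it is 0.005; at 5%, 0.264. The two-participant threshold would thus seldom be reached at low rates. The relatedness wording matters most for a death, where one case suffices.

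**The case against.** The strongest reply is that oversight does not rest on these triggers alone. H.3.9 sends grade 3 and above events to the SMC whatever their cause. Every death reaches the IRB within 7 days. The IRB and federal agencies may stop the study at any time. I.10 already has the investigators judge relatedness to procedures. Eligibility rules lower the procedural risk. All of this stands, and it rules out several stronger readings that a reader might infer:

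- **That a single grade 4 leukapheresis complication escapes because of the relatedness limit.** It does not. Both lists need two participants, so one grade 4 event triggers nothing whatever its cause.
- **That the SMC would hear nothing, or would hear late.** The reporting routes above exist. Whether H.3.9 reports carry a deadline depends on the manual of operations and the DAIDS reporting manual, which are not part of these documents.
- **That enrolment would have to continue after such a death.** No rule requires that. An automatic trigger is missing; the power to act is not.
- **That no end-of-study complication could count.** One judged at least possibly related to rIL-2 would. The exclusion is certain only for the baseline procedure.
- **That none of 40 procedures being able to trigger a pause measures the harm.** For events defined as purely procedural, zero follows from the definition.

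What the reply does not supply is any provision linking a procedure-related death, or repeated procedure-related severe events, to a pause or an SMC review. The scheduled reviews are no substitute: the interval is 6 months in G and about 3 months in I.3, and G allows the call to be forgone.

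**Conclusion.** The concern holds in limited form. The triggers in G and I.3 are narrower in causality than H.3.2 and I.10. A death caused purely by leukapheresis, grade 4 events of that cause in two or more participants, or under I.3 grade 3 events in three or more, brings no automatic pause or expedited SMC review. This applies to up to 20 baseline procedures without exception, and to up to 20 end-of-study procedures when the event is judged unrelated to rIL-2.

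The conclusion rests on reading study treatment as rIL-2, which the synopsis, H.3.7 and I.7.2 support. The further finding that H.3.2 misses both procedures rests on a per-participant reading of the treatment phase and on the D.2.10 schedule. The documents give no leukapheresis event rate, so the point concerns the scope of a safety rule and is not an estimate of harm. It should be corrected because it bears on participant safety and the correction is cheap.

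**What to change.** Reconcile G and I.3 with H.3.2 and I.10, so that the causality scope of the oversight triggers covers study procedures, including leukapheresis, as well as rIL-2. Reword the H.3.2 window so that it clearly includes both planned leukaphereses. In H.3.7, have the investigators record relatedness to study procedures alongside relatedness to rIL-2, which puts the I.10 assessment on the form.

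In the same amendment, reconcile G and I.3 on two further differences: the grade 3 trigger, which only I.3 contains, and the SMC review interval (6 months against about 3). C.2.1 and D.2.10 also need to agree on when the final sample is taken.

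The cost is amendment wording, one extra field on the adverse event form and possibly one more expedited review by the existing SMC. One limit remains: a pause in enrolment does not by its terms address end-of-study leukaphereses in participants already enrolled. The sponsor and SMC should state how those are handled after a trigger.
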